4.3 Software

All report outputs will be produced using SAS[®] version 9.4 or a later version in a secure and validated environment.

4.4 COVID-19 Impact

Some study procedures are permitted, within the protocol defined visit windows, to ensure safety of enrolled subjects and continuity of the follow-up visit schedule, due to circumstances when a subject is unable to return to the clinic due to the COVID-19 pandemic.

Nevertheless, subjects must be present in the office for the following assessments:

- PIH assessments (ODS, CC)
- PIH assessments (ODS, CCI

• CCI

Global COVID-19 pandemic ongoing during the course of the study can potentially impact the study. This section describes how the impact of COVID-19 will be reported.

4.4.1 COVID-19 Impact on Subject Disposition

Subjects who experience either screen failure or study treatment discontinuation or study discontinuation due to COVID-19 have the reason captured in the eCRF respectively on Randomization/Reason for Not Randomizing, End of Treatment form and End of Study form. Cases of screen failure or study treatment discontinuation or study discontinuation due to COVID-19 will be included in the summary of subject disposition and flagged in listings.

4.4.2 COVID-19 Impact on Visit Modality and Missed Visits

For each subject, eCRF Visit forms capture whether the missed visit or remote visit is due to COVID-19.

The number of subjects with missed visits or alternate visit modality (remote visit) due to COVID-19 will be summarized by visit and overall and will be listed.

4.4.3 Protocol Deviations due to COVID-19

Protocol deviations due to the COVID-19 pandemic will be collected per the study specific Protocol Deviation Specification. Major and minor pandemic related protocol deviations are identified within by using the term "COVID-19". Major COVID-19-related protocol deviations will be summarized as sub-categories under existing categories of protocol deviations (see Section 4.5.2). All major COVID-19 related protocol deviations and will be flagged. All PDs will be reviewed during the Data Review Meeting.

4.4.4 Prior/Concomitant Medications and Procedures related to COVID-19

Prior and Concomitant Medications and Procedures related to COVID-19 are captured in the eCRF respectively on Prior/Concomitant Medications form and Procedures form.

Medications and therapies used to treat COVID-19 associated medical history and adverse events will be flagged in the listing of prior and concomitant medications.

Procedures used to treat COVID-19 associated medical history and adverse events will be flagged in the listing of prior and concomitant procedures.

4.4.5 COVID-19 Impact on Efficacy Variables

Number of missing assessments due to COVID-19 will be reported in respective summary tables described in section 4.10 for the following parameters:

• Overall disease severity hyperpigmentation

CCI Effective Date: 26 Nov 19

CCL

4.4.6 Adverse Events related to COVID-19

Adverse events associated with COVID-19 are reported by investigators on Adverse Events form. All COVID-19 associated adverse events will be included in standard AE tables described in section 4.11.

An overview summary table of COVID-19 associated treatment-emergent adverse events (TEAEs) as described in section 4.11.3 will be provided for the Safety Population.

Listing of COVID-19 associated adverse events will be provided for all subjects in the Safety Population.

4.4.7 COVID-19 Impact on Local Tolerability Scores

Number of missing Local Tolerability Scores due to COVID-19 will be reported in the global summary table described in section 0.

4.4.8 COVID-19 Impact on Subjects Reported Outcomes

Number of missing subjects reported outcomes due to COVID-19 will be reported in respective summary tables described in section 4.12.1.

4.4.9 Overview of COVID-19 Impact

A by-subject listing with the following information:

- COVID-19 related study disruptions? [Yes/No]
- COVID-19 related study disruptions impacting efficacy? [Yes/No]
- COVID-19 related study disruptions impacting safety? [Yes/No]
- Description of how the individual's participation was altered by COVID-19 related study disruption

will be provided.

Number and percentages of subjects with at least one study disruptions due to COVID-19 will be included in the summary of subject disposition as follows:

- Subjects affected by COVID-19 related study disruptions
- Subjects affected by COVID-19 related study disruptions impacting efficacy
- Subjects affected by COVID-19 related study disruptions impacting safety

4.5 Study Subjects

4.5.1 Disposition of Subjects

A clear accounting of the disposition of all subjects who enter the study will be provided, from screening to study completion and will include the following summaries:

- Number of subjects screened for entry into the study (Analysis set: All Screened Subjects)
- Number and percentage of subjects excluded prior to randomization and major reason (Analysis set: All Screened Subjects)

- Number and percentage of subjects excluded prior to randomization due to COVID-19 and major reason (Analysis set: All Screened Subjects)
- Number and percentage of subjects randomized by treatment group and overall (Analysis set: All Screened Subjects)
- Number and percentage of subjects randomized who discontinued before treatment and major reason by treatment group and overall (Analysis set: All Subjects Randomized)
- Number and percentage of subjects randomized who discontinued before treatment due to COVID-19 and major reason by treatment group and overall (Analysis set: All Subjects Randomized)
- Number and percentage of subjects treated with at least one dose of study medication by treatment group and overall (Analysis set: All Subjects Randomized)
- Number and percentage of subjects withdrawing from study drug and reasons as specified on the eCRF for drug withdrawal per treatment group and overall (Analysis set: All Subjects Randomized)
- Number and percentage of subjects withdrawing from study drug due to COVID-19 and reasons as specified on the eCRF for drug withdrawal per treatment group and overall (Analysis set: All Subjects Randomized)
- Number and percentage of subjects completing the study by treatment group and overall (Analysis set: All Subjects Randomized)
- Number and percentage of subjects withdrawing from the study and reasons as specified on the eCRF for study withdrawal by treatment group and overall (Analysis set: All Subjects Randomized)
- Number and percentage of subjects withdrawing from the study due to COVID-19 and reasons as specified on the eCRF for study withdrawal by treatment group and overall (Analysis set: All Subjects Randomized)
- Number and percentage of subjects affected by COVID-19 related study disruption, affected by COVID-19 related study disruptions impacting efficacy and affected by COVID-19 related study disruptions impacting safety.

A by-subject listing of subjects' disposition details will be provided.

4.5.2 Accounting of Subjects

Number and percentage of subjects will be summarized by clinical visit and by analysis visit (Analysis set: All Subjects Randomized).

A by-subject listing of scheduled visits and a by-subject listing of unscheduled visits will be provided.

4.5.3 Protocol Deviations

Major protocol deviations and any action to be taken regarding the exclusion of subjects or affected data from specific analyses are defined in the project-specific Protocol Deviation Specification.

Number and percentage of subjects with at least a major protocol deviation by treatment group and overall and by type of deviation will be summarized (Analysis set: All Subjects Randomized)

1.0

A by-subject listing of all protocol deviations will be provided.

4.6 Analysis Sets

The efficacy summaries and analyses will be based on the **Intent-to-Treat (ITT) population** defined as all randomized subjects. If a subject is allocated the incorrect study drug as per the study randomization list, subjects will be summarized and analyzed 'as randomized' i.e., by randomized treatment group.

For the primary efficacy variable, a sensitivity analysis will be performed on the **Per Protocol (PP) Population** to assess the robustness of the study conclusions to the choice of population. The PP Population is defined as any subjects in the ITT population who had compliance to the study drug between 80% and 120% and assessments of the primary endpoint at Baseline and Week 24, without any major deviations that could have a significant effect on the efficacy of the study drug (e.g., errors in drug assignment, use of prohibited medications). Subjects will be summarized and analyzed 'as randomized' i.e., by randomized treatment group.

The safety summaries and analyses will be based on the **Safety Population**. The Safety Population is defined as comprising the ITT population subjects who applied/took the study drug at least once. If a subject is allocated the incorrect study drug as per the study randomization list, subjects will be summarized and analyzed 'as treated' i.e., by allocated treatment group.

Upon database release, protocol deviation and analysis populations outputs will be produced and reviewed. An analysis set classification meeting will be arranged to discuss the outputs and to decide which subjects and/or subject data will be excluded from certain analyses. Decisions made regarding the exclusion of subjects and/or subject data from analyses will be made prior to unblinding and will be documented and approved by Sponsor.

Number and percentage of subjects in each analysis population will be summarized by treatment group and overall, (Analysis set: All Randomized Subjects)

A by-subject listing of analysis populations details will be provided. This listing will be presented by treatment group and will include center, subject identifier, inclusion/exclusion flag for each population and reason for exclusion from each population. All subjects screened will appear on this listing. If subject data has been partially excluded, visit will also appear on this listing.

4.7 Demographic and Other Baseline Characteristics

Demographic and other baseline characteristics will be summarized by treatment group and overall. All summaries will be produced based upon the ITT population. Additional summaries of demographic and baseline characteristics will be produced based upon the Safety population if the ITT population and the Safety population do not include the same subjects.

4.7.1 Demographic characteristics

A summary of demographic characteristics will be presented and will include the following variables:

- age in years as a continuous variable
- age in years by class :<18, \geq 18
- gender

CCL

- ethnicity
- race

A by-subject listing of demographic characteristics details will be provided.

4.7.2 Baseline characteristics

A summary of baseline characteristics will be presented and will include the following variables:

- Fitzpatrick Skin Type score
- PIH Overall Disease Severity at Baseline

CCI		

A by-subject listing of baseline characteristics details will be provided.

4.7.3 Childbearing Potential Status, Methods of Contraception and Reproductive Status

A summary and a by-subject listing of Childbearing Potential Status, Methods of Contraception and Reproductive Status will be provided.

4.7.4 Medical History

Relevant medical history (past and current) will be coded using Medical Dictionary for Regulatory Activities (MedDRA) version 24.1 or higher.

Previous and concomitant relevant or major illness will be summarized by system organ class (SOC) and preferred term (PT).

A by-subject listing of medical history will be provided and present the primary SOC, PT and verbatim text. The listings will be sorted by treatment group, subject, primary SOC, PT and verbatim text.

4.8 **Prior and Concomitant Therapies**

The following two categories will be considered for previous and concomitant therapies:

- Drugs/therapies including, but not limited to, prescription, over-the-counter (OTC), birth control pills/patches/hormonal devices, vitamins, cleansers, moisturizers, sunscreens, herbal medicines/supplements, and homeopathic preparations.
- Medical and surgical procedures including, but not limited to, laser/radiation procedures, dermal fillers, X-rays (excluding dental X-rays), etc.

Prior and ongoing therapies started before the study and concomitant therapies will be coded using World Health Organization Drug Dictionary (WHODD) September 2021 Global B3. The therapeutic class will correspond to the second level of Anatomic Therapeutic Class (ATC) code.

CCI

GALDERMA R&D RD.06.SPR.204245

Prior and ongoing medical and surgical procedures started before the study and concomitant medical and surgical procedures will be coded using MedDRA Version 24.1 or higher.

Therapies start and stop dates will be compared to the date of first application of study medication to allow therapies to be classified as either Prior or Concomitant.

Therapies that start and stop prior to the date of first application of study medication will be classified as Prior.

Therapies that start before the date of first application of study medication and stops on or after the date of first application of study medication, as well as therapies that start after first application of study medication will be classified as Concomitant.

Therapies with missing or incomplete start dates will be classified on the basis of the imputed start date (see imputation rules of section 4.2.5). Therapies will be assumed to be Concomitant, unless there is clear evidence (through comparison of partial dates) to suggest that the medication started and stopped prior to the first dose of study medication.

Prior medications and concomitant medications will be summarized separately by therapeutic class and preferred name. These summary tables will be presented for each treatment group and overall based upon the ITT population.

Procedures will be classified as either Prior or Concomitant and summarized similarly to prior and concomitant medication by SOC and PT.

By-subject listings of prior and concomitant medications and of prior and concomitant procedures will be presented. Listings will be sorted by treatment group, subject, chronological start date, therapeutic class, preferred name and verbatim name.

4.9 Treatment Compliance

4.9.1 Study Duration and Treatment Duration

For randomized and treated subjects, study duration will be calculated relative to the reference start date (i.e., first treatment date) as Study Duration = End of Participation Date – First Treatment Date + 1.

For randomized but not treated subjects, study duration will be calculated relative to the reference start date (i.e., date of randomization) as Study Duration = End of Participation Date - Randomization Date + 1.

For randomized and treated subjects, treatment duration will be calculated relative to the date of first treatment as Treatment Duration = Last Treatment Date - First Treatment Date + 1.

Study duration and treatment duration will be summarized for each treatment group and overall based upon the ITT population.

4.9.2 Compliance and Drug Accountability

The compliance will be calculated for each visit and globally as:

Actual applications

Planned Applications – Missed Applications due to Prescribed Dose Reductions \times 100

CCL

For the overall compliance:

- Overall actual applications will be derived as the sum of actual applications at each visit. For treated subjects with no drug accountability information, overall actual applications will be calculated as Date of Last Treatment as collected in the End of Treatment form minus Date of First Treatment as collected in the End of Treatment form plus 1. If Date of Last Treatment is not collected in the End of Treatment form, overall actual applications will be set to 1.
- Overall planned applications will be derived as date of study completion/discontinuation minus date of baseline visit.
- Overall missed applications due to prescribed dose reductions will be derived as the sum of missed applications due to prescribed dose reductions at each visit.

Number and percentage of subjects compliant defined as having a compliance between 80% and 120% will be summarized by treatment group and overall.

Additionally, compliance expressed in percentage and by category (<80%; 80%-120%; >120%) will be summarized by visit and globally and will be presented for each treatment group and overall based upon the ITT population.

By-subject listings will be presented for compliance and drug accountability. .

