## 5.4.2 Instructions for Use – Study Drugs and Non-Investigational Products

Table 3: Guidelines for Using Study Drugs and Non-Investigational Products

[figure not shown]
	Trifarotene Cream				
	OR				
Trifarotene Vehicle Cream					
Study Drug Usage	
 
Apply a thin layer to the face once daily, in the evening. The face should be washed and patted dry, before use.
 
One pump actuation should be enough to cover the face (i.e., forehead, cheeks, nose, and chin).
 
				
	The Investigator may instruct alternate day regimen application of the topical study drug (detailed subject instruction will be provided) and re-evaluate at each visit to modify accordingly following the Baseline visit. Refer to Section 5.4.8 – Dose Modification of Topical Study Drug.				
	Non-Investigational Product Use Guidelines *				
Cetaphil® Gentle Skin C	Cleanser: Topical, wash face, twice daily, in the morning and evening.				
Cetaphil® Dermacontrol day, reapply every two h	Moisturizer SPF 30: Topical, apply after morning cleansing. If sun exposure during the nours.				
Cetaphil® Moisturizing Lotion: Topical, if extra moisture is needed, apply as needed.					
Duration of administrati	on for the above products: 24 weeks				

\* These are guidelines for non-investigational product use and will not be recorded as protocol deviations. Subjects will be counselled on the importance of using non-investigational products per the study guidelines, throughout the study. Compliance and protocol deviation reporting will apply only to study drug products. Alternative cleanser and moisturizers are not permitted, only the supplied non-investigational products to be used.

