### **5.4.8 Dose Modification**

If a subject experiences persistent skin dryness or irritation, the Investigator may consider a reduced application frequency for the topical study drug in the first 4 weeks of the study, for a maximum duration of 2 weeks. Subjects should be instructed to capture all missed topical applications in the dosing calendar. Sites will record the timing and details of a prescribed dose reduction for topical medication in source records.

Signs and symptoms of local cutaneous irritation will be considered as Adverse Events if they are severe enough to lead to permanent discontinuation of topical study drug or if they require the use of concomitant treatment including OTC products (other than moisturizers). Refer to Section 6.3.4 for further details on local tolerability assessment.

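### SAP 4.9.2 scores a treated subject with no drug accountability information as if the cream was applied every day, so unknown adherence can meet the PP compliance condition

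*SAP*

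**What the plan says.** SAP 4.9.2 defines compliance as actual applications divided by planned applications less those missed under a prescribed dose reduction, times 100. The overall figure is built as follows.

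- Numerator, main rule: "Overall actual applications will be derived as the sum of actual applications at each visit".
- Numerator, fallback: "For treated subjects with no drug accountability information, overall actual applications will be calculated as Date of Last Treatment" minus the date of first treatment plus 1, both dates from the End of Treatment form.
- Numerator, second fallback: "If Date of Last Treatment is not collected in the End of Treatment form, overall actual applications will be set to 1".
- Denominator: "Overall planned applications will be derived as date of study completion/discontinuation minus date of baseline visit". From this the prescribed missed applications are subtracted: "Overall missed applications due to prescribed dose reductions will be derived as the sum of missed applications" at each visit.

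The result is tabulated as below 80%, 80% to 120%, or above 120%. No category is listed for unknown compliance.

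SAP 4.6 admits to the PP population those ITT subjects who "had compliance to the study drug between 80% and 120" per cent, who have primary-endpoint assessments at Baseline and Week 24, and who have no major deviation likely to affect efficacy. Protocol 7.3.2 says the same. Neither requires the compliance figure to rest on recorded applications.

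Protocol 5.4.6.4 compares expected doses with those the subject entered in the dosing calendar. It contains no fallback.

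**The concern.** The fallback measures time on treatment. SAP 4.9.1 defines treatment duration by the same formula, last date minus first date plus one. For these subjects the SAP takes treatment duration, calls it the number of applications, and divides it by time in the study. The ratio is close to 100% for anyone whose last-treatment date is near the exit date, however often the cream was used.

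The PP analysis is meant to show the treatment comparison among subjects known to have used the product as planned. Admitting subjects on assumed adherence works against that purpose. The same figure also makes the compliance table look more favourable than the records support.

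There is also a mismatch within the ratio. Applications withheld by prescription are taken out of the denominator, but the fallback span still counts those days in the numerator.

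**Working it through.** The documents give no numerical compliance result to reproduce, so the check applies the SAP formulas to a 24-week completer.

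**Inputs**
- Target day for Week 24 is 169, with day 1 the first treatment day (SAP 4.2.2 and 4.2.6).
- The Week 24 visit window is ±5 days, so exit falls on day 164 to 174 (Protocol 5.1.1.2).
- PP limits are 80% and 120% (SAP 4.6).
- A dose reduction is allowed "in the first 4 weeks of the study, for a maximum duration of 2 weeks" (Protocol 5.4.8). On the regimen, Protocol Table 3 says: "The Investigator may instruct alternate day regimen application of the topical study drug". Fourteen days on alternate days means 7 missed applications.
- Assumptions: first dose on the baseline day, and study completion on the day of the Week 24 visit.

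**Fallback, exit on day 169**

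Planned = 169 − 1 = 168. Actual = last day − 1 + 1 = last day.

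| Last treatment | Calculation | Compliance | 80% to 120%? |
|---|---|---|---|
| Day 169 | 169/168 | 100.6% | yes |
| Day 168 | 168/168 | 100.0% | yes |
| Day 135 | 135/168 | 80.4% | yes |
| Day 134 | 134/168 | 79.8% | no |
| Date missing | 1/168 | 0.6% | no |

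Two completers with equally unknown adherence can thus score 100.6% and 0.6%, depending on whether one date field was filled in.

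**Across the visit window**
- Exit on day 164 (163 planned): 131/163 = 80.4% passes and 130/163 = 79.8% fails.
- Exit on day 174 (173 planned): 139/173 = 80.3% passes and 138/173 = 79.8% fails.

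The earliest passing last dose therefore lies between day 131 and day 139.

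**Prescribed dose reduction, exit on day 169**

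With 7 missed applications recorded, the denominator is 168 − 7 = 161.
- As written: 169/161 = 105.0%.
- With the same 7 days also removed from the span: (169 − 7)/161 = 100.6%.
- Pass threshold as written: 129/161 = 80.1% passes and 128/161 = 79.5% fails, so it moves from day 135 to day 129.
- Extreme case, all 14 days missed: 169/(168 − 14) = 169/154 = 109.7%, still below 120%.

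**The case against.** The strongest reply is that the case will seldom arise. Diary and compliance checks are scheduled at all eight post-Baseline visits, and product return and accountability at six. Someone with no information from any of them, yet with a Week 24 score and a late last-treatment date, should be rare. A subject whose records are absent because of early withdrawal will generally have no Week 24 score and fails PP on that ground. PP also excludes relevant major deviations. The classification meeting in SAP 4.6 reviews the populations before unblinding, and the Protocol Deviation Specification, which is not available here, may already exclude such subjects. All of this stands as a limit on size. It does not change the stated rule, and nothing in SAP 4.6 tells the meeting to disregard the derived figure.

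A second reply is that the SAP does not define drug accountability information, and the schedule lists product accountability and diary compliance on separate rows. If the term means returned product only, calendar records might exist for these subjects. The sentence stands as the exception to summing applications, which favours the reading used here but does not settle it. On the other reading the fallback would override records that exist, and the fix below covers that case too.

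A reader might infer more than the documents support:
- That partly recorded subjects are treated worse than wholly unrecorded ones. This requires an unrecorded interval to count as zero applications, a rule the SAP does not state.
- That exposure is misreported because SAP 4.11.1 assigns an unreturned pump its full nominal fill. The SAP states that assumption openly, it feeds one descriptive summary, and it does not enter the compliance formula.
- That the SAP 4.11 statement about not imputing data contradicts such conventions. It is a general sentence about observed-case summaries, and the specific rules govern.

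**Conclusion.** The point holds and is minor. The fallback gives about 100% compliance to a completer with no drug accountability information and a late last-treatment date, and at least 80% for any last dose from day 135. That meets the PP compliance condition without evidence of use and departs from the calendar basis in Protocol 5.4.6.4. The dose-reduction mismatch is a small inconsistency: it adds about 4 percentage points in the example (105.0% against 100.6%) and does not breach the 120% limit.

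The day limits assume a first dose on the baseline day and exit on day 169; within the visit window the threshold moves only between days 131 and 139. The number of subjects concerned cannot be determined from the documents and is probably small. The reach is the compliance tables and one of the four sensitivity analyses of the primary endpoint. A reader might infer that the primary result is at risk. It is not: that analysis uses all randomized subjects and no compliance figure. Nor do the documents show that PP membership would be altered in practice, because the Protocol Deviation Specification may already exclude such subjects.

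**What to change.** In SAP 4.9.2, use recorded dosing-calendar applications wherever they exist. Where none exist, set overall compliance to missing in place of both fallbacks (the date span and the value of 1), and report missing as its own category in the compliance table. In SAP 4.6, state that missing compliance does not satisfy the 80% to 120% criterion for PP. Removing the span also removes the dose-reduction mismatch.

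This takes SAP wording and programming only and leaves data collection as it is. The downside is a slightly smaller PP set.
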